7.1.2 Inclusion criteria

- Infants with a birth weight \leq 1000 Gram
- Admission to the neonatal ward in the first 24 hours of life
- Randomization on the respective study drug in the first 5 days of life

7.1.3 Exclusion criteria

Triplets or higher

Conjugated bilirubin > 1.5 mg/dl before inclusion to the study

Conditions associated with cholestasis independent of parenteral nutrition:

- Inborn errors of metabolism
- Viral Infections (cytomegaly virus, HIV, Hepatitis B, C)
- Immune mediated hemolytic disease (e.g. Rhesus incompatibility)
- Diagnosis of cystic fibrosis
- Primary cholestatic diseases of the liver

At follow up:

- Congenital neurological malformations and patients with chromosomal aberrations will be excluded from follow up analysis (except screening for adverse events)

7.1.4 Study duration

The interventional phase starts with randomization on the study drug in the first 5 days of life and ends with discontinuation of PN, typically after 6 weeks (mean 44 days +/- SD 34 days, personal data).

The follow up phase ends at 24 months (2 years) of corrected gestational age.

7.1.5 Withdrawal and replacement of subjects

Criteria for withdrawal

Premature discontinuation from the study is to be understood when the subject did not undergo End of Study (EOS) examination and / or all pivotal assessments during the study.

Subjects must be withdrawn under the following circumstances:

- at their parent's request at any time
- if the investigator feels it would not be in the best interest of the subject to continue
- if the subject violates conditions laid out in the consent form / information sheet or disregards instructions by the study personal
- if the subject is transferred to another hospital before parenteral nutrition is discontinued
- if the study drug was not provided < 80% of time as planned per protocol
- If an exclusion criterion is met, after inclusion to the study (except neurological malformation and chromosomal aberration which only leads to withdrawal from follow up analysis except screening for adverse events)
- death before day of life 28

In all cases, the reason why subjects are withdrawn must be recorded in detail in the CRF and in the subject's medical records. Should the study be discontinued prematurely, all study materials (complete, partially completed and empty CRFs) will be retained.

Follow-up of patients withdrawn from the study

In case of premature discontinuation after study drug intake, the investigations scheduled for the EOS visit will be performed 7 +/-4 days after study drug discontinuation. The subjects will be advised that participation in these investigations is voluntary. Furthermore, they may request that from the time point of withdrawal no more data will be recorded and that all biological samples collected in the course of the study will be destroyed.

Replacement policy

Patients withdrawn from the study < 28 days (outcome cannot be calculated) will be replaced and the next free subject number will be allocated. Drops outs will be included in the sample size. If patients are withdrawn from the study and the outcome can be calculated, (more than two blood samples taken), they will be considered in the intention to treat analysis (see chapter 10)

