8.1.4 Study drug premature permanent discontinuation

Study drug premature permanent discontinuation due to an adverse event

If the reason for premature permanent discontinuation of study treatment is an AE, the patient should have a "Premature End of Study (EOS)" visit with all the assessments performed before the study drug discontinuation, whenever possible.

Study drug premature permanent discontinuation due to another reason than adverse event

If the reason for premature permanent discontinuation of study treatment is not an AE, the patient should be withdrawn from the study (withdrawal of consent) and have the end of study (EOS) visit with all the assessments performed before the study drug discontinuation, whenever possible.

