8.5.4 Laboratory Tests

Blood counts and complete blood chemistry is routinely performed according to the local standard of care at the unit at least every 10 +/-4 days until discharge from hospital. No additional blood sampling or analyses will be performed in study subjects in comparison to standard of care of ELBW infants.

All laboratory parameters of interest for the study routinely performed are:

denomination	Variable	time of measurement
Conjugated bilirubin	mg/dL	every 7-14d until discharge
ALAT	U/L	every 7-14d until discharge
ASAT	U/L	every 7-14d until discharge
γ-glutamyltransferase	U/L	every 7-14d until discharge
Alkaline phosphatase	U/L	every 7-14d until discharge
Triglycerides	mg/dL	every 7-14d until discharge

Additional parameters used for the study

All additional parameters of interest are documented or produced routinely during the patient's admission to the unit or follow-up according to the local standard of care. No additional interventions will need to be performed.

denomination	Variable	time of measurement
Basic demographic data		
Sex	m/f	at birth
Gestational age	days	at birth
Twin	yes/no	at birth
Mode of delivery	caesarean/spontaneous	at birth

Prenatal steroids for lung maturation	yes/no	at birth
Birth weight	gram, Z Score	at birth
Birth crown heel length	cm, Z Score	at birth
Birth head circumference	cm, Z Score	at birth
Small for gestational age	yes/no	at birth
Apgar scores at 1, 5 and 10 minutes	0-10	at birth
Umbilical artery pH at birth	range 6.7 – 7.6	at birth

Growth and nutrition parameters

Time on parenteral nutrition	days	at discharge
Total amount of parenteral lipids	gram	at discharge
Enteral nutrition in 1 st first week of life	ml/day	day 0-6
Weight at discharge	gram, Z Score	at discharge from hospital
Crown heel length at discharge	gram, Z Score	at discharge from hospital
Head circumference at discharge	gram, Z Score	at discharge from hospital
Death > 28 days	yes/no	day of life 28 - discharge
(Death before 28 days = drop out)		
If death	day of life	day of life 28 - discharge

Neonatal (preterm) morbidities

Intraventricular hemorrhage Grad 3/4	yes/no	at discharge
Cystic periventricular leucomalacia	yes/no	at discharge
Chronic lung disease	yes/no	at discharge
Received steroids for chronic lung disease	yes/no	at discharge
Treatment for pulmonary hypertension (Sildenafil, iNO)	yes/no	at discharge
Culture proven sepsis	yes/no	at discharge
Necrotizing enterocolitis Bell's Stage ≥ IIa	yes/no	at discharge

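### Withdrawal from the study, not only from study drug, leaves it unstated whether bilirubin is still recorded, so later PNAC can be missed and counted as no event

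*Combined protocol and SAP*

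**What the plan says.** Section 7.1.5 introduces its list with "Subjects must be withdrawn under the following circumstances". Two entries matter here: the exposure rule, "if the study drug was not provided < 80% of time as planned per protocol", and "If an exclusion criterion is met, after inclusion to the study", from which only neurological malformation and chromosomal aberration are excepted. Transfer to another hospital before parenteral nutrition ends is also on the list.

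For a permanent drug stop not caused by an adverse event, section 8.1.4 says "the patient should be withdrawn from the study (withdrawal of consent) and have the end of study (EOS) visit". For a stop caused by an adverse event it asks for a premature end-of-study visit and does not use the word withdrawn.

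After withdrawal, section 7.1.5 provides that "the investigations scheduled for the EOS visit will be performed 7 +/-4 days after study drug discontinuation", and calls participation voluntary. The ordinary end-of-study examination is at discharge (8.5.3). Blood chemistry is routine in every infant "at least every 10 +/-4 days until discharge from hospital" (8.5.4), and the table there lists conjugated bilirubin every 7 to 14 days.

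The modified intention-to-treat (mITT) set (11.1) takes every infant with more than two blood samples, including those not observed for the full 18 weeks. For infants withdrawn before week 18, section 11.5 adds treatment duration as a covariable and a per-protocol analysis. Infants withdrawn before 28 days are replaced (7.1.5).

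**The concern.** The protocol does not separate stopping study drug from stopping outcome collection. PNAC needs two consecutive conjugated bilirubin values above 1.5 mg/dl. An infant with normal values at withdrawal and more than two samples enters the mITT set as free of PNAC. If recording ends there, later PNAC is a missed event, although the values that would show it are in the hospital record.

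The early work-up does not close the gap. A first raised value found there is one value, and the definition needs two. The treatment-duration covariable does not close it either: it is measured after randomisation and cannot restore events that were never recorded.

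At stake are some loss of power and, if withdrawal differs between the arms, a shift in the primary comparison of unknown direction. Infants withdrawn before 28 days and replaced may also leave the randomised comparison.

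**Working it through.** **Inputs from the documents.** PNAC 25% (Intralipid) and 10% (SMOFLipid); 100 per group; 80% power; two-sided 0.05; 22% drop-out; 122 per group planned (synopsis, 11.2). The 22% is mortality, and section 7.1.1 expects no other drop-out.

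**The plan's own figure.** For a chi-square test without continuity correction, with mean proportion 0.175:

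n = [1.96·√(2·0.175·0.825) + 0.8416·√(0.25·0.75 + 0.10·0.90)]² / 0.15² = 99.5, so 100 per group. Power at 100 is 80.2%. The figure reproduces.

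**Baseline used here.** 122 × 0.78 = 95 per arm after the expected deaths.

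Power = Φ[(p₁ − p₂ − 1.96·SE₀)/SE₁], where SE₀ = √(2p̄(1 − p̄)/n) and SE₁ = √((p₁(1 − p₁) + p₂(1 − p₂))/n).

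At 95 per arm: Φ[(0.15 − 1.96 × 0.05513)/0.05405] = 78.1%. The drop from 80.2% to 78.1% comes from how the sample was inflated for drop-out (100 × 1.22 rather than 100/0.78). It is not part of this point.

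**Assumptions.** The documents give neither a non-death withdrawal rate w nor the share of withdrawn infants' events that would come after withdrawal. I take that share as one half, assume withdrawn infants carry average risk, and assume they stay in the mITT set. The observed rate is then p × (1 − 0.5w).

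| Withdrawn, Intralipid / SMOFLipid | Observed rates | Difference (points) | Power at 95 per arm |
|---|---|---|---|
| none | 25.0% / 10.0% | 15.0 | 78.1% |
| 5% / 5% | 24.4% / 9.8% | 14.6 | 76.8% |
| 10% / 10% | 23.8% / 9.5% | 14.3 | 75.5% |
| 15% / 15% | 23.1% / 9.3% | 13.9 | 74.1% |
| 15% / 5% | 23.1% / 9.8% | 13.4 | 70.4% |
| 25% / 5% | 21.9% / 9.8% | 12.1 | 63.1% |
| 5% / 25% | 24.4% / 8.8% | 15.6 | 83.1% |

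Example, 15% / 5%: 0.25 × (1 − 0.075) = 0.2313 and 0.10 × (1 − 0.025) = 0.0975. The difference is 0.1338.

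**No true effect** (25% in both arms, 100 per arm, 5% against 15% withdrawn). With half of later events missed, the false difference is 1.25 points and the rejection rate 5.5%. With all of them missed, it is 2.5 points and 7.1%.

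**Which infants are affected.** An infant with PNAC already confirmed and more than two samples stays in the mITT set as a case, whatever exclusion condition is found later. A case can be lost only from the per-protocol set, or where too few samples were taken. An infant with exactly two samples is not covered: section 11.5 excludes fewer than two, and section 11.1 includes more than two.

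**The case against.** The strongest reply is that no sentence says recording stops. Section 7.1.5 lets parents ask that no further data be recorded, which suggests that recording may otherwise go on. Section 10.1 has all participants followed to 24 months, and section 12.1.1 requires a case report form for those who do not complete. This stands in part: truncation is a strong inference, not a stated rule. It rests on the early end-of-study work-up and on sections 11.1 and 11.5, which provide for incompletely observed infants. The text is ambiguous on a matter that determines the primary endpoint.

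Three stronger readings are tempting, and the documents do not support them.

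- A reader might infer that the later-exclusion rule removes cases from the main comparison, since the listed conditions are other causes of cholestasis and may be sought once bilirubin is raised. Sections 7.1.5 and 11.1 keep confirmed cases with more than two samples in the mITT set.
- A reader might infer that withdrawal will differ by arm because high triglycerides interrupt or reduce the emulsion (8.1.3). That is possible but unquantified. The interruption is 24 hours, and with a mean of 44 days on parenteral nutrition (7.1.4), 20% of the time is 8.8 days. Nothing shows that many infants would miss that much, or more in one arm.
- A reader might take every drug stop as forced withdrawal. Section 8.1.4 adds withdrawal of consent in brackets to the non-adverse-event case, which may mean that the parents decide, and it does not order withdrawal after an adverse event.

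The plan also already keeps evaluable withdrawn infants and runs both mITT and per-protocol analyses.

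**Conclusion.** The point holds as a gap in the plan that should be fixed, with medium confidence. The protocol requires study withdrawal in situations where only study drug need be in question, does not say that bilirubin is recorded afterwards, and analyses these infants on what was seen up to then. Later PNAC can therefore count as no event, although routine values exist to discharge.

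The size is modest if withdrawals are few and balanced: about 1 to 4 points of power for 5% to 15% in each arm. It is larger, and of undetermined direction, if they are unbalanced. Every withdrawal rate and the one-half share are assumptions, so the table shows sensitivity and is not a forecast. The documents do not support a claim that the primary comparison will be biased.

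**What to change.** 1. In 7.1.5 and 8.1.4, define study drug stopped and withdrawn from study as separate states. State in 8.1.4 what the bracketed withdrawal of consent means.
2. Unless parents refuse further data use, record every routine conjugated bilirubin value to discharge after study drug stops, and analyse the infant in the arm to which it was randomised. Apply this also to infants stopped before 28 days, whether or not another infant is enrolled in their place.
3. Use the 80% exposure rule and later-found exclusion conditions only to define the per-protocol set.
4. Reconcile the wording of the exposure rule: its double negative, read literally, points to well-exposed infants. Say also whether the 80% is counted over the whole course.
5. State how an infant with exactly two samples is handled (11.1 against 11.5).

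The cost is protocol and SAP wording plus transcription of laboratory values already taken in routine care. No extra blood sampling is needed and no treatment rule changes. Data may remain incomplete for infants transferred to another hospital.

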8.1.1 Dosage and administration

Initial dose:	1 g/kg/d (= 5 ml/kg/d)
Maintenance dose:	3 g/kg/d (=15 ml/kg/d)
Route of administration:	Intravenous
Duration:	As long as parenteral nutrition is needed

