8.1.3 Study drug interruption or discontinuation

The investigator must temporarily interrupt or permanently discontinue the study drug if continued administration of the study drug is believed to be contrary to the best interests of the patient. The interruption or premature discontinuation of study drug might be triggered by an AE, a diagnostic or therapeutic procedure, an abnormal assessment (e.g., laboratory abnormalities), or for administrative reasons, in particular withdrawal of the patient's consent.

Hypertriglyceridemia: The study drug will be interrupted for 24 hours at triglyceride levels > 400 mg/dl or down titrated at triglyceride levels of 251-400 mg/dl. Control measurements of triglyceride levels will be performed in the next 24-72 hours to control for successful normalization of triglyceride levels under parenteral nutrition.

The reason for study drug interruption or premature permanent discontinuation must be documented in the CRF.

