8.1.9 Procedures to assess subjects compliance

Whether the IMP or comparator where administered correctly will be followed from the documentation in the electronic patient documentary system used at the neonatal ICU.

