11.1 Analysis sets

Two different analysis sets are defined:

(Modified) Intention to treat set

This analysis set includes all subjects where the outcome can be calculated (more than two blood samples taken), even though the subject was not observed the full 18 weeks.

Per-protocol set

This analysis set comprises all subjects who were observed the full 18 weeks, received the study drug as planned and did not violate the protocol in a way that might affect the evaluation of the effect of the study drug on the primary objective, i.e., without major protocol violations.

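### The mandatory exposure criterion for withdrawal in section 7.1.5 is garbled: read literally, it withdraws fully treated infants and keeps those with little exposure

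*Combined protocol and SAP*

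**What the plan says.** Section 7.1.5 gives a list of circumstances in which withdrawal is compulsory. Among parental request, transfer to another hospital, a newly met exclusion criterion and early death stands this one: "if the study drug was not provided < 80% of time as planned per protocol".

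The related text is as follows.

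- **Planned exposure.** Section 8.1.1 sets the duration of treatment as "As long as parenteral nutrition is needed". Section 7.1.4 says that parenteral nutrition stops "typically after 6 weeks (mean 44 days +/- SD 34 days, personal data").
- **What follows from withdrawal.** The reason goes into the CRF, and end-of-study investigations are offered. Section 7.1.5 also says: "Patients withdrawn from the study < 28 days (outcome cannot be calculated) will be replaced". For withdrawn infants whose outcome can be calculated it says that "they will be considered in the intention to treat analysis"; sections 11.1 and 11.5 agree.
- **Per-protocol set.** Section 11.1 asks for infants who "received the study drug as planned and did not violate the protocol in a way that might affect the evaluation". It gives no numeric exposure limit. Section 11.4 leaves the definition of major and minor deviations, and their link to the analysis sets, to the SAP.

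The 80% figure appears only in section 7.1.5. Nothing else in the documents restates or corrects it.

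**The concern.** The sentence joins a negative to a less-than sign. Taken at face value, it makes adequate exposure the trigger for withdrawal and lets near-absent exposure pass. This is an operative instruction with no discretion attached, so site staff and monitors cannot follow it literally and must correct it silently.

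What is at stake is which infants are recorded as withdrawn for low exposure. If the SAP later takes this threshold as the meaning of planned treatment, per-protocol membership would be affected as well.

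**Working it through.** **Background figure.** The plan's own number is 100 per group (section 11.2), for 25% against 10%, two-sided alpha 0.05 (the synopsis gives the sidedness) and 80% power. With the mean proportion (0.25 + 0.10)/2 = 0.175:

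n = [1.960 × √(2 × 0.175 × 0.825) + 0.842 × √(0.25 × 0.75 + 0.10 × 0.90)]² / 0.15² = (1.053 + 0.444)² / 0.0225 ≈ 99.6, rounded up to 100.

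Power at 100 per group is 80.2%. The exposure criterion is not an input, so this figure is unaffected.

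**Truth table for the criterion.** Let *e* be the share of planned time on study drug.

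- Intended rule: withdraw if e < 80%.
- Literal reading A, *it is not the case that provision was below 80%*: withdraw if e ≥ 80%.
- Literal reading B, *the time without drug was below 80%*: withdraw if 1 − e < 80%, that is, e > 20%.

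| e | Intended | Reading A | Reading B |
|---|---|---|---|
| 100% | keep | withdraw | withdraw |
| 90% | keep | withdraw | withdraw |
| 80% | keep | withdraw | withdraw |
| 79% | withdraw | keep | withdraw |
| 50% | withdraw | keep | withdraw |
| 20% | withdraw | keep | keep |
| 10% | withdraw | keep | keep |
| 0% | withdraw | keep | keep |

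Reading A is the exact opposite of the intended rule. Reading B agrees with it only between 20% and 80%. Both are wrong at 80% and above and at 20% and below.

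**The same in days.** Assume that planned time equals the days of parenteral nutrition, and take the mean course of 44 days from section 7.1.4.

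- 8 missed days: e = 36/44 = 81.8%, so the intended rule keeps the infant. Time without drug is 8/44 = 18.2%, so A and B both withdraw.
- 9 missed days: e = 35/44 = 79.5%, so the intended rule withdraws for the first time.
- 40 missed days: e = 4/44 = 9.1%, so the intended rule withdraws. Time without drug is 40/44 = 90.9%, so A and B both keep the infant.

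These figures show where an 80% limit falls. They do not estimate bias.

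**Two possible sources of the error.** Deleting the negative gives withdrawal if e < 80%. Keeping it and turning the sign round gives withdrawal if not (e ≥ 80%), which is the same rule. The documents do not show which slip occurred, and the correction does not depend on it.

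**The case against.** The strongest answer is that this is a copy-edit. The criterion sits in a list of failures, the per-protocol definition points the same way, and withdrawing every well-treated infant would empty the trial. A looser reading, with the negative attached to the plan and the percentage describing the shortfall, even gives the sensible rule. All of this stands. It shows that the intent is recoverable and that the effect is small. It does not make the sentence right.

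A reader might infer three stronger things, and the documents support none of them.

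- **That the primary analysis is distorted.** Inclusion in the modified intention-to-treat set depends on blood samples, not on this criterion, and withdrawn infants with a calculable outcome stay in.
- **That replacement is materially affected.** Replacement is limited to withdrawals before 28 days without a calculable outcome. The share of planned time is final only when parenteral nutrition ends, on average at 44 days. Infants with short courses could reach that point earlier (the SD is 34 days), but section 8.5.4 continues routine bilirubin sampling until discharge. A missing outcome would therefore mostly reflect death or transfer, which are separate criteria.
- **That the per-protocol set is defined by the faulty threshold.** Section 11.1 gives no number, and section 11.4 assigns the matter to the SAP. The link is an inference.

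**Conclusion.** The criterion is wrong as written, and the severity is minor. Both straightforward literal readings require withdrawal at full exposure and none at 20% or less. The intended rule is withdrawal below 80% of planned exposure, and staff would probably apply it that way. On that footing no sample size, power or modified intention-to-treat result changes. What remains is formal withdrawal status and possibly per-protocol membership.

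The conclusion about the wording rests on the text alone. The illustration in days assumes that planned time is the duration of parenteral nutrition and that the course has the mean length. The documents do not say how many infants would fall below 80%, so the number affected cannot be stated.

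**What to change.** Replace the criterion in section 7.1.5 with: *if the study drug was provided for less than 80% of the time planned per protocol*.

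Nothing else has to change. The sponsor may wish to say how mandated pauses count. Any such clause should cover only the triglyceride rule in section 8.1.3 ("The study drug will be interrupted for 24 hours at triglyceride levels > 400 mg/dl"). That section also covers interruptions for adverse events and for administrative reasons, and counting those as planned exposure would weaken the threshold. The clause is optional: one 24-hour pause is 1/44 = 2.3% of a mean course. Whether 80% also defines adequate treatment for the per-protocol set should be left to the SAP, as section 11.4 provides.

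The cost is one sentence. Section 8.1.9 already states that correct administration "will be followed from the documentation in the electronic patient documentary system used at the neonatal ICU", so no new data are needed.

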STATISTICAL METHODOLOGY	
Primary Endpoint PNAC (definition see efficacy endpoint)
 
Null and alternative hypotheses: H₀ : The percentage of PNAC in group 1 (investigational drug) equals group 2 (comparative drug) H₁: The percentage of PNAC in group 1 (investigational drug) does not equal group 2 (comparative drug)
 
Sample size calculation A sample size estimation using a χ^2-test indicated that 200 infants (100/group) are required to detect a 15% difference (10% in group 1 vs. 25% in group 2) with a power of 80% and a two-sided significance level of 0.05. The estimated drop out rate is 22%. Therefore, a sample size of 122 patients per group is planned. For sample size estimation, data were assumed to be independent.
 
Statistical methodology Main analysis set(s) A χ^2-test will be used for analysis of the primary outcome PNAC. Additionally, the effect of treatment and other relevant influence factors (i. e. duration of parenteral nutrition, birth weight, necrotizing enterocolitis) on the primary endpoint will be analyzed using a logistic regression model with

	
stepwise selection. In case of twins, the analysis will be carried out 1) as mentioned above, but only including the firstborn and 2) by calculating a generalized linear model with mother as random factor.
 
Other endpoints
 
Bailey Scales of Infant Development III at 12 and 24 months: Differences in the scores of psychomotor development and neurocognitive development, respectively, between the groups will be analyzed by repeated measures ANOVAs, also accounting for confounder factors (e.g. birth weight, ...). In case of twins, the analysis will be carried out 1) as mention above, but only including the firstborn and 2) by calculating a mixed model with mother and child as random factor. In case of too many drop outs, descriptive statistics will be carried out.
 
For Gross Motor function measurements at 12 and 24 months, descriptive statistics will be conducted.

--	--

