11.2 Sample size considerations

Data investigating the incidence of PNAC in our unit showed an incidence of 25 % from 2007-9 (unpublished data). We considered a difference of 15% between the groups (incidence of PNAC: 25% for Intralipid and 10% for SMOFLipid, respectively) as a clinically relevant effect. A sample size estimation based on a χ^2 -test indicated that 200 infants (100/group) are required to detect a difference of 15% between the groups with a power of 80% and a significance level of 0.05. The estimated drop out rate is 22%. Therefore, a sample size of 122 patients per group is planned. For sample size estimation, data were assumed to be independent.

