11.6.3 Safety and tolerability endpoints

Hypertriglyceridemia: Peak level in mg/dl

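### Deaths before day 28 are replaceable drop-outs under a rule that conflicts with the sample-count rule, and neither mortality by arm nor an analysis counting death is specified

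*Combined protocol and SAP*

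**What the plan says.** - Section 7.1.5 lists death before day 28 among the circumstances that require withdrawal. Its replacement policy reads: "Patients withdrawn from the study < 28 days (outcome cannot be calculated) will be replaced and the next free subject number will be allocated". The same paragraph then takes withdrawn infants into the intention-to-treat analysis if their outcome is calculable, which it defines as having more than two samples.
- Section 8.5.4 repeats the label: "Death before 28 days = drop out". The death variables listed there run only from day 28 to discharge.
- Section 11.1 defines the modified intention-to-treat set: "This analysis set includes all subjects where the outcome can be calculated (more than two blood samples taken"). The per-protocol set needs the full 18 weeks of observation. Section 11.5 excludes infants with fewer than two samples and keeps those withdrawn before week 18 who have more than two.
- Section 7.1.1 takes drop-out entirely from mortality (22% in 2010). It subtracts 18 of 81 infants a year before the primary analysis, leaving 63, and expects no other cause of drop-out. Section 11.2 carries the 22% into the sample size.
- The synopsis gives no safety endpoint. Section 11.6.3 gives one: "Hypertriglyceridemia: Peak level in mg/dl". Sections 11.6.1 and 11.6.2 do not treat death as an outcome or a competing event.

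**The concern.** Death follows randomisation, and treatment may affect it. If infants who die early leave the analysis, the primary test compares survivors, and randomisation does not guarantee that survivors are alike in the two arms. Enrolling another infant restores the number but not the comparability. An emulsion that changed early mortality could then appear to change PNAC, and no analysis specified here would show a reader that this had happened.

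The rules also conflict. One is based on calendar age (day 28) and the other on the number of samples, and they can classify the same infant differently. The infants affected are those whose place in the primary analysis should be least open to later choice.

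**Working it through.** **1. The plan's own figures.** Inputs from section 11.2 and the synopsis: "incidence of PNAC: 25% for Intralipid and 10% for SMOFLipid, respectively", "with a power of 80% and a two-sided significance level of 0.05". With pooled variance and no continuity correction:

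n = [1.96·√(2 × 0.175 × 0.825) + 0.842·√(0.25 × 0.75 + 0.10 × 0.90)]² / 0.15² = 99.5, so 100 per group (power 80.2%).

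This reproduces the stated requirement. The 122 per group is 100 × 1.22; dividing by 1 − 0.22 gives 129. Removing 22% from 122 leaves about 95 per arm (power 78.1%).

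**2. Can PNAC be reached before day 28?** A conjugated bilirubin above 1.5 mg/dl before inclusion is an exclusion (section 7.1.3), so PNAC needs two post-baseline values. With baseline on day b (0 to 5) and interval g, the second falls on day b + 2g:

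- g = 6: day 12 to 17
- g = 10: day 20 to 25
- g = 14: day 28 to 33

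So it can over much of the permitted range, but not at the longest interval. On the Table 1 schedule (weeks 2 and 4, each ± 4 days) the second post-baseline sample falls on day 24 to 32. There, an infant who dies before about day 24 has at most two samples including baseline.

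**3. Where the rules collide.** The sections do not say whether the baseline sample counts.

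- If it counts, the third sample falls on the days in step 2, so an infant dying shortly before day 28 can be due for replacement and also belong to the modified intention-to-treat set.
- If it does not count, the third sample falls on day b + 3g: day 18 to 23 at g = 6, but day 30 to 35 at g = 10. An infant with two raised values and no third sample then meets the endpoint, falls outside section 11.1 (more than two) and is not excluded by section 11.5 (fewer than two).

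**4. How many deaths?** At 22% of 244, 0.22 × 244 ≈ 54 (about 27 per arm). Expected PNAC cases among about 190 survivors are 95 × 0.25 + 95 × 0.10 ≈ 33. The share of deaths before day 28 is not given.

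**5. Size of possible bias (all values assumed).** Suppose treatment has no effect on PNAC and average mortality is 22%. One arm loses a further share s of infants, whose PNAC risk is r; those who would survive in either arm have 25% risk. With a = 1 − 0.22 − s/2, the survivor rate in the arm without the extra deaths is (a × 0.25 + s × r)/(a + s), against 25% in the other:

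- s = 5 points, r = 50% to 75%: 26.6% to 28.1%, a bias of 1.6 to 3.1 points
- s = 10 points, r = 50% to 75%: 28.0% to 31.0%, a bias of 3.0 to 6.0 points
- r = 25%: no bias

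The bias favours the arm with more deaths. In the most extreme case (10 points, 75%), the chance of a significant result in that direction is about 15% instead of 2.5%.

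**6. Which analysis corrects it?** Two further assumed scenarios, again with no effect on PNAC and with every death preceding detection:

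| Mortality; PNAC risk of infants whose survival differs by arm | Survivors only | All randomised, deaths as non-cases | PNAC or death |
|---|---|---|---|
| 22% v 30%; 60% | 25.0% v 21.0% | 19.5% v 14.7% | 41.5% v 44.7% |
| 22% v 15%; 50% | 25.0% v 27.1% | 19.5% v 23.0% | 41.5% v 38.0% |

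First row: 0.78 × 0.25 = 0.195; 0.195 − 0.08 × 0.6 = 0.147; 0.147/0.70 = 0.210; 0.22 + 0.195 = 0.415; 0.30 + 0.147 = 0.447. Second row: 0.195 + 0.07 × 0.5 = 0.230; 0.230/0.85 = 0.271; 0.15 + 0.230 = 0.380.

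Scoring early deaths as non-cases widens the distortion (4.0 to 4.8 points; 2.1 to 3.5 points). Only the composite points against the arm with more deaths.

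**7. Power of the composite.** Assume mortality m equal by arm and independent of PNAC, so the rates are m + (1 − m) × 0.25 and m + (1 − m) × 0.10:

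- m = 22%: 41.5% v 29.8%, power 47.9% with 122 per arm; 262 per arm needed for 80%
- m = 15%: power 58.6%; 202 per arm
- m = 10%: power 67.6%; 164 per arm

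For mortality itself at 22% with 122 per arm, the 95% interval for the difference has half-width 1.96·√(2 × 0.22 × 0.78/122) = 10.4 points.

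**The case against.** Several stronger readings are tempting, and the documents do not support them.

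- *Every early death is discarded.* Section 7.1.5 itself keeps withdrawn infants with more than two samples, and its parenthesis can be read as limiting replacement to infants without a calculable outcome. What stands is a conflict between two rules, plus the loss of early deaths with fewer samples.
- *The stated ground is simply false.* It is sound for many early deaths, particularly on the Table 1 schedule. It fails for some.
- *Death is the largest post-randomisation outcome.* The 22% is one year's mortality at the unit. It is not split at day 28 and may include deaths before randomisation. About 27 deaths per arm is therefore an upper figure, and it is close to the 24 PNAC cases expected among 95 control infants.
- *Deaths will go unreported, and each is replaced by a survivor.* Withdrawal reasons go into the CRF, deaths are serious adverse events (sections 9.2 and 10.1), and section 11.4 defers data displays to an analysis plan. Mortality by arm is unspecified, not shown to be withheld. A replacement infant may die too.
- *The primary result is biased.* The mortality gaps and PNAC risks in the illustrations have no source in the documents. The 4.0-point example is about 0.6 of a standard error (about 6.3 points with 95 and 85 infants).

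These limit the claim without removing it: capturing deaths is not a planned comparison, and nothing specified would show whether mortality was equal and non-selective.

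**Conclusion.** The concern holds in limited form. The day-28 rule rests on a ground that is not always true, contradicts the sample-count rule, and leaves infants with exactly two samples unclassified. Early deaths with too few samples leave the primary comparison, while the documents specify neither mortality by arm nor an analysis in which death counts.

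The possible bias is a few percentage points under the assumed values, set against a planned effect of 15 points. It depends on mortality that differs by arm and is related to PNAC risk, and on how many deaths fall before day 28. It is zero if mortality is equal and non-selective. The defect in the rules does not depend on those assumptions.

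**What to change.** 1. Remove the day-28 replacement rule from section 7.1.5 and the matching label in section 8.5.4. Reconcile sections 7.1.5, 11.1 and 11.5 on one definition of a calculable outcome, stating whether baseline counts and how exactly two samples are handled.
2. Keep every randomised infant under the original allocation, and count PNAC reached before death as a case.
3. Do not silently score early deaths without PNAC as non-cases. Prespecify a PNAC-or-death or competing-risk analysis of all randomised infants beside the primary test. Given its lower power, make it supportive rather than primary.
4. Record death from randomisation to discharge, and add all-cause mortality by arm, with a confidence interval, to section 11.6.3.

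The cost is wording changes and two extra tables. No new data are needed. There will be somewhat fewer fully observed infants than if deaths were replaced. Dropping replacement also stops the plan providing for the same deaths twice, once by replacement and once by inflating the sample size.
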